3. STUDY OUTCOMES

3a. Primary outcomes

Aim 2: Stepped-wedge randomized controlled trial (RCT)

The primary outcome for this study is **adolescent retention in HIV care**, defined as:

 Return for 1st follow-up visit after first enrollment visit OR return for follow-up visit after a 're-engagement visit' among adolescents who had previously been lost to follow-up (LTFU) • Retention in care for ANY follow-up visit within 3 months among adolescents currently enrolled in HIV care (which can be referred to as "actively enrolled")

Description:

First follow-up visit after enrollment visit: The number and proportion of adolescents who return to clinic within 3 months of an enrollment visit

Follow-up visit after re-engagement in care among LTFU adolescents: Lost to follow-up is defined as no clinic record for at least 3 months, and no record of death or transfer to another facility. Among adolescents who return to clinic after LTFU, we will collect the number and proportion of adolescents who return for a subsequent visit within 3 months.

Return for follow-up among those currently enrolled in care: To evaluate whether the SPEED intervention may result in better adherence to visit schedule among adolescents currently enrolled in HIV care (i.e. not newly enrolled or previously LTFU), we will also measure return for any follow-up visit within 3 and 6 months.

3b. Secondary outcomes:

Aim 1: Pilot testing of case scripts and establishment of competency

- Final case scripts
- Numeric scores on HCW checklist
- Proportion of HCWs with pass/fail scores
- Numeric scores on actor feedback checklists
- Numeric scores on HCW satisfaction survey
- Numeric scores on HCW self-rated competency survey

Aim 2: Stepped-wedge randomized controlled trial

In addition to the primary outcomes, the RCT will have several secondary outcomes, summarized in in Table 1:

Analyses of *process outcomes* to understand intervention mechanism will include:

- Pre/post-measures of HCW and patient satisfaction
- Pre/post-measures of HCW competency scores
- Associations between HCW competency scores and care outcomes
- Associations between HCW competency scores and adolescent satisfaction outcomes

• Exit interviews in a purposeful sample of HCW participants at the end of the trial

Table 1. Summary of process outcomes, exploratory outcomes, and indicators in Aim2 RCT

Process Outcomes	Indicator	Source
HCW competency	Mean HCW scores per clinic	Faculty graded scores
		Exit interviews

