6. SPEED STUDY INTERVENTION

This study is evaluating a clinical training intervention utilizing standardized patients (SPs) that is anchored in social learning and behavioral theories [31, 32]. Standardized patients (SPs) are trained actors that work with health care providers in mock clinical training encounters, with a focus on improving communication skills and empathy. Through SP encounters, HCWs learn through cycles of concrete experiences, reflection, conceptualization, and active experimentation in a safe and controlled setting. We hypothesize that improved communication skills, competency, and empathy that HCWs will gain through this training will motivate adolescent patients to stay engaged in HIV care, including initiating and adhering to ART.

The clinical training intervention will consist of a combination of didactic sessions and SP encounters. Provider participants will receive orientation to the SP actor methodology as well as content related to communication skills and adolescent care. The intervention training schedule will be planned to minimize disruption to clinic operations.

For each wave of six clinics in the RCT, we estimate that it will take about 2 weeks (not more than 4 weeks) to train all HCWs in the Nairobi/Kiambu and Western Kenya sites. This timeframe will vary based on HCW availability and travel.

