A CONSORT diagram, adapted for a stepped-wedge design [34] will be used to show the number of HCW-participants within clusters and flow of randomized stepped wedge clusters though the five time periods. We will report the number of clinics selected for inclusion, assignment to intervention or control at each time period, and the number of HCWs trained at each facility. We will report number of excluded clusters and any reasons for exclusion. No replacement will be used. Facility-specific information – adolescent patient volume, number of HCWs and presence of any adolescent-specific service (peer groups, clinics etc.) prior to the intervention – will be grouped by clinic and recorded. Baseline values of primary and process outcomes, and socio-demographic characteristics of adolescents and HCWs will be presented in a descriptive table.

We will use generalized linear mixed models (GLMM), which are more efficient than paired ttests and linear mixed models (LMMs) in the analysis of cluster RCTs when the size of clusters is unequal [32] to compare the probability of an adolescent returning to clinic after enrollment visit OR second visit after >3 months LTFU between the intervention and control periods [35]. To estimate the effect of the intervention (*Xij*) on the individual level, we will use a GLMM model with a Poisson distribution and robust standard errors, allowing for random effects for clusters (*ui*) and fixed effects for time (*j*). This approach models individual level outcomes, adjusts for temporal trends and accounts for correlation of outcomes within a cluster (clinic). We will estimate adjusted risk ratios (ARR), adjusted risk differences (ARDs) and 95% confidence intervals at the 5% significance level (two-sided). Adjusted risk ratios will be estimated for secondary outcomes: initiating and adherent to ART (≥80% in the dosing period by pharmacy records), 12-month retention in care; viral suppression (<100 copies/ml, <1000 copies/ml), and referred for ancillary services (family planning and TB screening). Models will be adjusted for facility type, patient volume, and exposure to prior adolescent health interventions (c).

The equation for a generic model is: $Y_{ijk} = \beta_0 + \beta j_{time} + \beta_{effect} X_{ij} + \beta c X ij$, $ui + \varepsilon ij$

- Analyses of process outcomes to understand intervention mechanisms will include:
 - Mean HCW competency (passing score proportion per clinic) before and after the intervention

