 - Association between mean HCW competency scores per facility and adolescent satisfaction scores
 - Associations between mean adolescent satisfaction scores and 1) retention in care (binary), 2) referral to APS services (binary), 3) ART adherence (binary or mean percent), and 4) viral suppression (binary) comparing the exposed and unexposed periods.
- Evaluation of temporal trends: Temporal trends that change over time (e.g. introduction of new HIV treatment guidelines, COVID-19) and potentially impact study outcomes can lead to a biased effect estimate in a stepped-wedge trial design [34]. To assess this possibility, we will repeat the primary analyses including an interaction term between a time indicator (e.g. coded as 'pre' versus 'post' policy/program change) and the variable for the main effect. A p-value for the interaction <0.1 will be evidence of interaction. We will report these results in a separate table showing any differences in intervention effect by this temporal change.

- Lag effects of SPEED intervention: Because the effect of the intervention may not be immediate or it may diminish over time, we will evaluate these possibilities in two ways. HCWs may take time to put skills they learned in the training into practice. In addition, trained HCWs may decrease or stop using these new skills. Intervention lag will be modeled by re-coding the first month after the intervention as a control period, as recommended by Davey *et al.* [34]. We will model the reduction of the intervention effect over time by using a fractional term for the coefficient of primary effect estimate, which will have a value of 1 (assumes 100% exposure) and get smaller at each time step (e.g. 75%, 50%, 25%).
- Qualitative analysis of exit interviews: Qualitative data from the HCW exit interviews will be coded in Atlas.ti. Data will be analyzed by two reviewers using thematic analysis according to the interview guide. These results will be utilized to complement results from the structured HCW satisfaction surveys.

Cost-effectiveness Analysis (CEA) and Cost Utility Analysis (CUA)

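### Does pooling newly enrolled and re-engaged adolescents in the primary model, with no analysis by entry type, call for a change to the plan?

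*Combined protocol and SAP*

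**What the plan says.** Section 3a makes retention the primary outcome. Its first part is return after an enrolment visit "OR return for follow-up visit after a 're-engagement visit' among adolescents who had previously been lost to follow-up (LTFU"). The description beneath it defines the two proportions separately, each as a number and a proportion returning within 3 months. On the gap that makes a patient re-engaged it says: "Lost to follow-up is defined as no clinic record for at least 3 months". Adolescents already in care have their own outcome, used to examine "whether the SPEED intervention may result in better adherence to visit schedule among adolescents currently enrolled in HIV care".

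Section 12c then fits a single Poisson mixed model to "compare the probability of an adolescent returning to clinic after enrollment visit OR second visit", with fixed period effects, a random clinic intercept and robust standard errors. The adjustment is "Models will be adjusted for facility type, patient volume, and exposure to prior adolescent health interventions". Entry type is not a covariate, a stratum or an interaction.

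The further analyses of the primary effect deal with timing only. For temporal trends, "we will repeat the primary analyses including an interaction term between a time indicator". For lag, "Intervention lag will be modeled by re-coding the first month after the intervention as a control period". A third lets the effect decay. Section 11 lists enrolment status and visit dates among the extracted record items, so entry type can be derived.

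**The concern.** The mix could move with the training itself. Section 6 expects that better skills "will motivate adolescent patients to stay engaged in HIV care". If that happens among patients already in care, fewer of them build up a 3-month gap, and fewer can later be counted as re-engaged. The primary denominator would then respond to the intervention. Period effects remove only changes common to all clinics, and the clinic intercept removes only stable differences between clinics. A mix change timed to each clinic's crossover passes through both.

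If re-engaged patients return less often than new ones, a shrinking re-engaged share raises the pooled risk ratio even when nobody's chance of return has changed. A growing share lowers it and could hide part of a real effect. No planned model separates the two, so the meaning of the primary result would be at stake.

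**Working it through.** **The plan's own figure.** Inputs from sections 5f and 12a: I = 24 clinics, T = 5 periods, 4 waves of 6, return 0.75 rising to 0.90, coefficient of variation 0.25, two-sided 5%. Hussey-Hughes variance:

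var = Iσ²(σ² + Tτ²) / [(IU − W)σ² + (U² + ITU − TW − IV)τ²]

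with U = 60, W = 1,080, V = 180, τ = 0.25 × 0.75 = 0.1875 and σ² = 0.825 × 0.175 / n.

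- n = 5: SE 0.0542, power 79.1%. This reproduces the stated minimum of 5 for 80% power.
- n = 6 (the number that section 12a multiplies up to 720): SE 0.0497, power 85.4%.
- The design risk ratio is 0.90/0.75 = 1.20, so its log is 0.182.

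**Simple size of a mix effect.** With return unchanged in both groups, the pooled difference is (fall in re-engaged share) × (new return − re-engaged return). New return is 75% (section 12a). The re-engaged rates and the shares are assumptions.

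| Case | Re-engaged return | Share | Difference | Ratio |
|---|---|---|---|---|
| A | 60% | 40 to 30% | 0.10 × 0.15 = 1.5 points | 0.705/0.690 = 1.022 |
| B | 55% | 40 to 25% | 0.15 × 0.20 = 3.0 points | 0.700/0.670 = 1.045 |
| C | 50% | 50 to 30% | 0.20 × 0.25 = 5.0 points | 0.675/0.625 = 1.080 |

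These ratios assume the whole change happens at crossover. That fits the mechanism poorly, because patients lost before training go on re-engaging after it.

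**In the stepped-wedge model, half the change in the first period after training and all of it later.** Pooled risk ratio with no effect in either group:

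- Expected values with clinic effects: A 1.011, B 1.022, C 1.040. Without clinic effects: 1.015, 1.031, 1.056.
- Simulation of the planned model (2,000 trials per case, 6 records per clinic and period): 1.017, 1.034, 1.050. Rejection is 5.2%, 7.0% and 8.0%, against 5.9 to 6.1% with no shift (Monte Carlo SE 0.5 to 0.6 points). Only C stands out.
- For A and B the range is 1.011 to 1.034. On the log scale that is 0.011/0.182 = 6% to 0.033/0.182 = 18% of the design effect. The standard deviation of the log risk ratio is 0.104, so the shift is at most about a third of one standard error at this sample size.

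**How demanding the cases are.** Hold new enrolments constant and compare the odds of being re-engaged before and after:

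- A: 0.667 to 0.429, so the re-engaged count falls 36%.
- B: 0.667 to 0.333, a fall of 50%.
- C: 1.000 to 0.429, a fall of 57%.

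The no-effect cases need training to cut disengagement by that much among patients in care while doing nothing for new or re-engaged patients seen by the same staff.

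**When training works in both groups (true ratio 1.20) and the share falls.** Pooled ratio: A 1.21 to 1.22, B 1.23 to 1.24, C 1.25 to 1.27. In A and B the conclusion hardly changes. In the opposite direction, a share rising from 30 to 50% with 50% return in the re-engaged gives 1.14 to 1.16; that needs 1.000/0.429 = 2.3 times as many re-engaged patients.

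**Whether adjustment would settle it.** Suppose the share falls from 40 to 25% and, because the more reliable returners no longer drop out, return among those who still re-engage falls from 55 to 45% by selection alone.

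- Pooled: (0.75 × 0.75 + 0.25 × 0.45) / (0.60 × 0.75 + 0.40 × 0.55) = 0.675/0.670 = 1.01.
- Standardised to the control mix: (0.60 × 0.75 + 0.40 × 0.45)/0.670 = 0.630/0.670 = 0.94. The model with an entry-type term gives 0.95 to 0.96.

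Here the adjusted and standardised figures suggest harm where there is none.

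**Precision by entry type.** If 6 records split evenly, n = 3 gives SE 0.068 and power 59% per group. Treating the groups as independent, two equal effects can differ by 1.96 × √2 × 6.8 = 19 points by chance. The change in share has SE 5.9 points (n = 6, share 40%, coefficient of variation 0.25 assumed).

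**The case for a change.** The best argument for acting is that it would be cheap and would guard against selective reporting. The data are already extracted, the primary model and sample size would stay as they are, and a split by entry type chosen after the results are known would carry less weight than one named beforehand. The separate proportions in section 3a are raw figures, unadjusted for clinic and period, so they do not amount to effect estimates. The mix distortion also does not shrink as records accumulate.

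Much of this stands. Section 12c names no analysis by entry type, the mechanism is plausible, and a reader of the pooled ratio alone could not separate the two routes. It does not show that a planned rule gives a wrong result. The intervention is delivered to clinics, randomised by clinic and analysed by intention to treat, so overall return among those who present is a coherent target. Section 6 states a hypothesis about patients in general, not about patients of a given entry type. If training changes nothing, the mix does not follow crossover and the test keeps its size. Extra models would not settle the interpretation either, because disagreement between pooled and adjusted estimates does not show which one is misleading. A rule restricting the conclusion whenever they differ could be set off by chance at these cell sizes.

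**Conclusion.** No change to the plan follows. Section 12c is an overview that leaves out a description analysts can supply from data already specified: numbers, shares and return proportions by entry type, period and training status, with any ratios by entry type read as supportive and imprecise. The pooled model is valid and should stay primary.

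The size of any mixing cannot be derived from the documents. Under moderate assumed shifts, phased in, it is about 1 to 3% in the risk ratio against a design value of 1.20. An assumed fall in share from 50 to 30% gives 4 to 6%, or 8% if it all happens at crossover. It is zero if the two groups return at the same rate, and the sign can go either way. These figures rest on assumed re-engaged return of 50 to 60% and the assumed shares above; only the 75% return, the coefficient of variation, the record counts and the design come from the plan. Data showing a large change in mix tied to training would limit how the primary result is described, but would not make the planned analysis wrong.

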5. STUDY ENROLLMENT AND WITHDRAWAL

5a. Study sites

The pilot phase will recruit health workers from Kenyatta National Hospital (KNH) in Nairobi, Kenya. The randomized controlled trial (RCT) will enroll health workers from up to 24 clinics that provide adolescent HIV care services in Nairobi and Western Kenya.

5b. Study population

The SP intervention involves a training program for HCWs who provide clinical services to adolescents living with HIV. Enrolled HCWs include clinical officers, psychologists (where available), doctors, and nurses. Additional cadres may be included, depending on their roles at the site, if they provide direct clinical services to adolescents. The study will enroll adolescent clients at each study site to assess outcomes of patient satisfaction, however adolescent retention and clinical outcomes will be assed via a de-identified audit of clinic electronic medical records (EMR).

Justification for involvement of adolescents: In sub-Saharan Africa, adolescents are at high risk for acquiring HIV, have poor HIV testing coverage, and are at high risk for poor treatment adherence. The purpose of this research is to improve adolescent HIV care. Collection of data about adolescents is necessary to determine the effectiveness and cost-effectiveness of this intervention aimed at improving adolescent HIV care.

5c. Participant inclusion criteria

To be eligible for this study, an individual or clinic must meet the criteria listed in Table 2 below. Eligible clinics must have at least 40 adolescents enrolled in care, a current EMR system, and no other special adolescent interventions. The eligibility criteria for the pilot phase is the same as for HCWs in the RCT. Health care worker participants must be 18 years of age or older, employed at trial sites and provide clinical services to adolescents. Adolescent records will be abstracted among 10-24 year olds enrolled in HIV care. Adolescent clients between the ages of 10-24 presenting for HIV care at enrolled sites will be eligible to complete patient satisfaction surveys.

5d. Site/Participant exclusion criteria

Facilities will be excluded if they do not meet inclusion criteria. A facility may also be excluded if anything would prevent the complete conduct of the training intervention at that site and/or the collection of outcome measures.

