7. STUDY PROCEDURES

Study procedures for the SPEED study consist of a pilot phase, which aims to test training materials and establish competency scores for participating providers; and a randomized trial phase, which will implement and evaluate the SP training intervention.

Note on recruitment, hiring, and training of SP actors

We will contract with a professional Kenyan casting agency to identify and train 6-7 actors over 18 who are able to portray adolescent cases ages 14 - 19. These actors will be part of the study staff and are not participants.

The actors will be trained on each adolescent patient case by a behavioral expert before the pilot phase. They will also be trained in human participants protections because of their contact with study participants (HCW participants). Actors will sign confidentiality agreements to ensure that they do not discuss the SP encounters, and other identifying information, to people outside of the study.

Actors will receive annual refresher training in the case scripts. The Study Team will monitor the actors' attendance at all HCW trainings, and report any problems to the casting agency.

7a. Pilot Phase

Development of adolescent case scripts

We have analyzed in-depth interviews of HIV-positive adolescents enrolled in an ongoing study on HIV testing and counseling at KNH to develop the case scripts which the actors will portray. Each case describes medical and social history of the adolescent, and the primary concern at that visit which the HCW must identify. The cases were developed to reflect a range of issues that may affect adolescent patients seeking HIV care, including around disclosure, depression, fertility desire, sexual behavior and sexuality, and gender-based violence. There are male and female cases, ranging in ages between 14 and 19.

Materials piloting and competency assessment

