using an Excel spreadsheet. These data will be collected at baseline assessment. Cost data will be updated, as needed, at the end of the trial.

Data sources from adolescents

- Clinic records: De-identified adolescent clinic records from the EMR system will extracted at baseline, and at the end of each wave to assess primary and clinical outcomes, according to our data use agreement with NASCOP. Data from each pull will capture all records until the previous data pull. Examples of data will be visit dates, enrollment status (newly enrolled or existing), date of birth/age, sex, viral load and CD4 counts, pharmacy records, and referrals to family planning/TB/STI services.
- Adolescent satisfaction, cost, and sexual behavior surveys: Anonymous post-visit surveys will be conducted with adolescents using electronic tablets. These surveys will be conducted at baseline and at the end of each wave in all sites. Information will include basic demographics (age, schooling), type of service received/reason for visit, satisfaction with services received, perception of judgment by the health HCWs, and intent to return for services. Questions will also ask about direct and indirect costs associated with seeking care that the facility (e.g. cost of transportation, lost wages). The last section of the survey will be self-administered and ask questions about sexual behavior and sexual partners using electronic tablets. These surveys will be conducted at immediately after the satisfaction and costs surveys.

Data Management Responsibilities

A dedicated data team will be responsible for the entry, management, and monitoring of study data, in accordance with standard operating procedures. The Nairobi data team will communicate frequently with the Seattle-based statistical team for reporting, data cleaning, study monitoring, and interim analyses. Study data uploaded to the secure study cloud server using Open Data Kit (ODK). Open Data Kit is a secure, web-based application designed by UW faculty to support data capture for research studies. The software provides 1) an intuitive interface for validated data entry; 2) automated export procedures for seamless data downloads; and 3) procedures for importing data from external sources.

Data Capture and Storage Methods

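### The retention model adjusts only for clinic-level characteristics, although age and sex are already extracted; adding them is a cheap, modest improvement

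*Combined protocol and SAP*

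**What the plan says.** Section 12c specifies a Poisson mixed model with robust standard errors, "allowing for random effects for clusters (*ui*) and fixed effects for time (*j". It describes the model this way: "This approach models individual level outcomes, adjusts for temporal trends and accounts for correlation of outcomes within a cluster (clinic". The covariate sentence is: "Models will be adjusted for facility type, patient volume, and exposure to prior adolescent health interventions (c".

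Section 5c sets the population: "Adolescent records will be abstracted among 10-24 year olds enrolled in HIV care". Section 11 lists the record fields to be extracted, including "enrollment status (newly enrolled or existing), date of birth/age, sex, viral load and CD4 counts".

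The only stated analytic use of adolescent characteristics is in Section 12c: "socio-demographic characteristics of adolescents and HCWs will be presented in a descriptive table". Neither the primary model nor any sensitivity analysis includes age, sex or another adolescent-level covariate.

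On patient volume, Section 5f defines a two-level stratum for randomisation, split at the median of 73 enrolled. Section 11 has the facility survey record patient volume at baseline and again at the end of each wave. Section 12c does not say which of these enters the model, and its equation indexes the covariate term by clinic and period.

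**The concern.** The model is individual-level, but every named adjuster is a property of the clinic. The model already has a clinic random effect and fixed period effects, so the training effect is estimated largely within clinics. A clinic characteristic that does not change over time can add only so much to that comparison. Individual characteristics that predict return would reduce the residual variance whatever the cell size.

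The first part of the primary outcome concerns newly enrolled and re-engaging adolescents, so each clinic-period cell holds largely different people. Clinic and period terms remove stable clinic differences and common drift. They do not remove a change in age or sex mix specific to one clinic.

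The volume covariate raises a smaller, related matter. If a value recorded after training is used, it could itself be affected by the intervention, because better retention raises the number in care.

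At stake are some precision and some robustness, using data the trial will already hold.

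**Working it through.** **Inputs.** Sections 8 and 12a give 24 clinics in 4 waves of 6, 5 periods, control return 75%, a 15% difference, coefficient of variation 0.25, and two-sided α of 0.05. I read the difference as absolute (75% to 90%), because that reading reproduces the plan's figures. Then:

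- τ = 0.25 × 0.75 = 0.1875, so τ² = 0.03516
- σ² = 0.825 × 0.175 = 0.1444, using the mean of 0.75 and 0.90

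**Formula.** This is the Hussey-Hughes variance, with s = σ²/n for n records per clinic and period:

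Var = I·s·(s + T·τ²) / [(I·U − W)·s + (U² + I·T·U − T·W − I·V)·τ²]

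- I = 24, T = 5
- U = 6 × (4+3+2+1) = 60
- W = 6² + 12² + 18² + 24² = 1,080
- V = 6 × (16+9+4+1) = 180
- I·U − W = 360
- U² + I·T·U − T·W − I·V = 3,600 + 7,200 − 5,400 − 4,320 = 1,080

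**Reproducing the plan.** With n = 6, s = 0.02406. The numerator is 24 × 0.02406 × (0.02406 + 0.17578) = 0.1154. The denominator is 360 × 0.02406 + 1,080 × 0.03516 = 46.63. Var = 0.002475 and SE = 0.0497. Power = Φ(0.15/0.0497 − 1.96) = 85.4%.

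Five records give 79.1%, so 6 is the smallest number reaching 80%, and 6 × 24 × 5 = 720 as stated. With 20 clinics, 7 records give 84.1%, and 7 × 20 × 5 = 700 as stated. At 40 records power exceeds 99%, as stated.

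**Adding individual covariates.** Replace σ² by σ²(1 − R²), where R² is the share of within-clinic outcome variance explained by age and sex. R² is an assumption.

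| Assumed R² | SE, n = 6 | SE reduction | Power, n = 6 | SE, n = 40 |
|---|---|---|---|---|
| 0 | 0.0497 | – | 85.4% | 0.0199 |
| 1% | 0.0495 | 0.5% | 85.8% | 0.0198 |
| 2% | 0.0493 | 0.9% | 86.1% | 0.0197 |
| 5% | 0.0486 | 2.4% | 87.0% | 0.0194 |

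To place that range: for two equal age groups whose return rates differ by g, R² = 0.25·g²/0.1444. A 10-point gap gives 1.7%, a 15-point gap 3.9% and a 20-point gap 6.9%.

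**Comparison with a clinic covariate.** Suppose a time-constant clinic covariate halves τ². The effect variance then falls by 5.5% at n = 6 and 1.3% at n = 40. An R² of 2% to 5% cuts the variance by about 2% to 5% at either size. Clinic covariates are therefore not inferior at the plan's minimum cell size; individual covariates do more only in large cells.

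**Case mix.** If the share of an age group shifts between exposed and control cells, beyond what clinic and period terms absorb, the estimate moves by shift × gap. A 10-point shift with a 10-point gap moves it by 0.10 × 0.10 = 1 point; 20 by 20 gives 4 points. The SE is about 5 points at n = 6 and 2 points at n = 40. These inputs are illustrative; the documents report no such shift or gap.

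**The case against.** The strongest reply is that the planned analysis is valid as written. Clinics are randomised, and clinic and period terms deal with stable differences and common trends. Age and sex are optional covariates worth a percent or two of the standard error. At the plan's minimum of 6 records per cell, a good clinic covariate may do as much or more; at 40 records, power is already above 99%. All of that stands, and it sets the size of the point.

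Three stronger readings are tempting and should not be adopted:

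- *The estimate is biased by case mix.* Chance imbalance in age and sex is already reflected in the standard error; it is not a second harm on top of wider intervals. Only clinic-specific shifts over time would matter beyond that, and the documents show none.
- *The effect is diluted because the scripts cover a narrower age range.* Section 7a does say "There are male and female cases, ranging in ages between 14 and 19", against records from ages 10 to 24. Dilution would need the training to work less well outside those ages. Section 6 describes general communication skills and empathy, and nothing ties the benefit to the scripted ages. A power figure for that scenario would rest on invented inputs, and adding age as a covariate would not cure dilution anyway.
- *Covariates can be added with no thought to the estimand.* The risk ratio is collapsible, but if the effect varies by age the adjusted ratio is a weighted summary. Section 12c also promises adjusted risk differences, which a log-link model yields only after standardisation.

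It is also fair to say that age and sex are not the only omissions. Region, a stratification factor in Section 5f, and new versus re-engaged status are absent from the adjusters too. That does not weaken the case for age and sex.

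**Conclusion.** The point holds as a modest, low-cost improvement. The named adjusters are all clinic-level, age and sex are already in the extract, and no effectiveness model uses them. The expected precision gain is about 0.5% to 2.4% of the standard error, or 0.4 to 1.6 power points at 6 records per cell (85.8 − 85.4 and 87.0 − 85.4). There is also some protection against clinic-specific changes in mix.

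This rests on an assumed R² of 1% to 5%, the plan's own design inputs, and the Hussey-Hughes approximation on the risk-difference scale in place of the planned Poisson model. The sample size argument in Section 12a is unaffected, and neither bias nor an inflated error rate has been shown. The unspecified timing of patient volume is a gap in the wording that the same edit can close.

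**What to change.** In Section 12c, for the primary and secondary retention models:

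- Add age band at the index visit and sex as individual-level covariates, with the bands stated in advance.
- State a simple rule for missing age or sex.
- State that the adjusted risk difference is obtained by standardising model predictions over the observed covariate distribution.
- Define patient volume as the pre-randomisation stratum in Section 5f (above 73, or 73 and below), so that no post-training value enters the model.

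If the sponsor wants it, an estimate for ages 14–19 against the other ages can be listed, labelled descriptive or exploratory.

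The cost is a few lines of SAP text and no new data. The wording should be fixed before outcome data are examined, so that the covariate choice cannot be questioned later.
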